# **Procedures Manual**

## Mama Bear Procedures manual Table of Contents page

## The purpose of the Mama Bear study is:

- to learn what kinds of support will help women meet their goals for breastfeeding and weight management after their baby is born
- to understand how breastfeeding and weight loss after a baby is born affects the health of mothers and their baby.

## **Mama Bear Study Activities Timeline**

Funding is 4/1/16-3/31/18 (with extension through 3/31/19)

	Time	Location	Activities (Staff Responsible)	Incentive
1	~28 weeks	NCO Clinic	
 
Pre-screening (N)
 
Eligibility, consent, weight, blood, urine (DC) & (N if time permits)
 
	\$20
2	28-32 weeks	Phone	Baseline survey data collection (DC)	N/A
		Randon	nization into Intervention Group or Usual Care Group	
3	32-36 weeks	Home or NCO Clinic *	
 
Intro to program, breastfeeding support * (CHW)
 
	\$30
		NCO Clinic	• Usual Care group (DC) & (N if time permits)	φ30
4	Birth		
 
All participants receive a congratulations letter and a Baby Bear board book via mail ([name])
 
	N/A
5	1-3 days postpartum	Home *	
 
Breastfeeding support, self-care tips* (CHW)
 
	N/A
6	~6 weeks postpartum	NCO Clinic	
 
Weight & Survey (DC, CHW) & (N if time permits)
 
Intro to mobile app* (DC, CHW) & (N if time permits)
 
	\$50
7	~20 weeks Postpartum	Home	Data collection to include measured weight (DC)	\$50

Kev

## 10/9/2017

## Mama Bear Incentive Plan for Participants in Both Study Arms (Intervention and Usual Care)

- 1. Enrollment: \$20 gift card + Mama Bear water bottle
- 2. Phone Survey: \$30 gift card
- 3. Soon after baby is born: Baby Bear board book (or notebook customized with Mama Bear logo)
- 4. ~6 week (4-8 week) postpartum clinic visit: \$50 gift card
- 5. ~20 week postpartum clinic or home visit: \$50 gift card

Additional Incentives for the Intervention Participants

- 1. Diapers and wipes (at early postpartum visit)
- 2. Bathroom scale (at 6 week postpartum visit)
- 3. Small "prizes" for using the online platform

## Mama Bear Clinic Recruitment

Guidelines for Nurses

Procedures:

#### A. Obtaining Informed Consent

- 1. Approach women presenting for prenatal care who meet the following criteria:
  - o African American
  - o 24-32 weeks gestation
  - o Scheduled for the one hour glucose challenge test this visit
  - o Single gestation
  - o No known fetal or chromosomal anomalies
  - Fluent in English and able to complete consent process
- 2. Ask permission to speak with them about a study that they might enjoy being a part of.
- 3. If a woman agrees to learn more about the study, provide her with the fiver
- 4. Script:
- 5. If the woman gives verbal agreement after this explanation, have her read the consent, and sign two consent forms. One will be given to the study participant, and the other one will be kept in her study file.
- 6. Have the participant sign the Gift Card Voucher and provide her with the \$30.00 gift card. Record the card on the Gift Card Distribution Form. Then complete all parts of the enrolment interview on the iPad in REDCap.
- 7. Explain to the participant that she will be contacted within the next week by a Mama Bear staff member from Henry Ford, who will conduct an interview over the phone. Confirm with patient that it is ok to leave a message (not sure if this is necessary but usually a good idea since this is related to her pregnancy). After that, she will be mailed \$20 in cash and some information about what she can expect next from the study.
- B. Obtaining Weight, Body Composition, Blood and Urine Specimens (for all handling of biological fluids, use gloves, and employ good hand washing techniques)
  - 1. Weight and Body Composition
    - a. Utilize the Tanita research study scale provided to measure the participant's weight and body composition.
    - b. Select "One-Step" Mode and input required data:
      - Enter weight of clothing- 1.0 kg (preset)
      - o Enter Study ID number
      - o Enter Body type- "Standard"
      - o Enter Gender- Female
      - o Enter age
      - o Enter height
    - c. Have the participant remove any outerwear garments (coat, hat, scarf, gloves), and remove her socks or stockings.
    - d. In the presence of the participant, clean the foot pads on the scale with alcohol wipes e. Have her step on the scale with her bare feet.
    - f. Print results and record the weight and body composition on the data collection form on the study iPad.
  - 2. Blood
    - a. Use the labels provided to write the ID number, date and time of the blood collection
    - b. Place one label on the red top tube, and one on the lavender top tube.
    - c. Hand both tubes to the participant ask her to take them with her to the lab so that her blood can be collected in these tubes at the same time that she is getting her blood drawn for the blood sugar test.
    - d. When the participant returns with the blood filled tubes, place them in a specimen collection bag, seal, and place the bag in the refrigerator.
  - 3. Urine
    - a. Use the label provided to write the ID number, date and time of the urine specimen collection.
    - b. Place the label on a urine vial provided for the study.
    - c. Have the participant hand you the cup with her freshly voided urine once she steps out of the restroom.
    - d. Pour a small amount of that urine into the pre-labelled urine vial and cap tightly.
    - e. Return the original cup of urine for testing with the dipstick.
    - f. Place the study urine vial in the bio-storage bag, close and seal, and then put the urine specimen into the refrigerator.

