#### C. Transporting Specimens

- 1. Towards the end of the work day, call the [name] lab contact number to inform the staff that Mama Bear study specimens will be delivered. Give an approximate time of arrival.
- 2. Place all research specimens collected for the day in the cooler provider.

Version Number 1 Date

[figure not shown]

3. Transport the specimens, by car, to [name] and pull into a space along the curb in front of the entrance. Call the lab the notify them of your arrival. Carry the specimen into the front lobby and hand to the lab representative.

Version	Number 1
---------	----------

(alternative: Mana Bear 031017\_4) The Mama Bear Flyer with description Mama Bear 031017\_4

The Mama Bear flyer (as shown below) is used by nurses when approaching patients in the clinic to see if they are interested in meeting with research staff. For more information, see Mama Bear Recruitment Procedures, Section A 3.

Mama Bear helps moms reach their breastfeeding goals and lose weight after giving birth.

Help moms like you have a healthy future. Join the Mama Bear research study today! Call: [contact] Email: [contact]

Front

ne as headle

- B. Obtaining Weight, Body Composition, Blood and Urine Specimens (for all handling of biological fluids, use gloves, and employ good hand washing techniques)
  - 1. Weight and Body Composition
    - a. Utilize the Tanita research study scale provided to measure the participant's weight and body composition.
    - b. Select "One-Step" Mode and input required data:
      - o Enter weight of clothing- 1.0 kg (preset)
      - o Enter Study ID number
      - o Enter Body type- "Standard"

- o Enter Gender- Female
- o Enter age
- o Enter height
- c. Have the participant remove any outerwear garments (coat, hat, scarf, gloves), and remove her socks or stockings.
- d. In the presence of the participant, clean the foot pads on the scale with alcohol wipes
- e. Have her step on the scale with her bare feet.
- f. Print results and record the weight and body composition on the data collection form on the study iPad.
- 2. Blood
  - a. Use the labels provided to write the ID number, date and time of the blood collection
  - b. Place one label on the red top tube, and one on the lavender top tube.
  - c. Hand both tubes to the participant ask her to take them with her to the lab so that her blood can be collected in these tubes at the same time that she is getting her blood drawn for the blood sugar test.

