#### Equipment: Tanita SC-240 (see Fig. 7)

**NOTE:** Total body water of participants will be measured using leg-to-leg bioelectrical impedance analysis. "In this system, two footpad electrodes (pressure contact) are incorporated into the platform of a precision electronic scale. A person's measurements are taken while in a standing position with the electrodes in contact with bare feet. The body monitor/analyzer automatically measures weight and then impedance. Computer software (a microprocessor) imbedded in the product uses the measured impedance, the subject's gender, height, fitness level, age (which have been programmed), and the weight to determine body fat percentage based on equation formulas." (Tanita website: http://www.tanita.com/en/tanita-publications/)

Figure 1. Tanita SC-240 for measurement of BIA and weight.

**Examinee Preparation:** Administer the questions in Measured Anthropometry in REDCap to determine if the participant meets any of the exclusion criteria. If the participant is pregnant or has a pacemaker or automatic defibrillator, they should be excluded from the BIA assessment as indicated by REDCap. NOTE: False teeth and hearing aids do not have to be removed. NOTE: Participants can drink reasonable amount of water before the BIA measurement to avoid dehydration.

**NOTE:** If participant is unable to independently stand on the BIA machine with both feet flat, she will not be able to participate in this part of the study. If the reason she cannot participate in the BIA measurement is apparent or volunteered by the participant, e.g. foot is in a cast; include this information in the comment field in the Measured Anthropometry section of REDCap.

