#### **Measurement Method:**

- Step 1. Administer BIA screening questions (R section 'Measured Anthropometry' in the main questionnaire) to make sure if the participant will be eligible for BIA measurement. Weight and BIA are measured at the same time as components of the one-time output method of the Tanita SC-240 instrument.
- Step 2. Before the BIA measurement, open the Tanita Health Ware software.
- Step 3. Sync the scale and computer
  - Open Tanita Health Ware software
  - Select "Done" from the User Profile menu that appears
  - Turn on the BIA scale. You should see a flashing "0 kg" on the screen.
    - If the scale is not in kilograms, press and hold "Enter/Zero"
      - Use the up/down arrows until it flashes "SET 5"
      - Press "Enter/Zero"
      - Use the up/down arrows until you see "0. KG"
      - Press "Enter/Zero"
      - Turn off the BIA scale
      - Turn on the BIA scale. You should now see "0 kg" flashing.

- Choose 'File'
  - o Choose Health Ware Options
  - o Choose SC-240 from the list of possible units
  - o Click "control scale remotely"
  - o Click "connect" and step on scale when it beeps
  - Remain on scale until the computer indicates that it is successfully communicating with the scale
  - o Click "ok" and then "ok" again to exit this menu

If this method *does not work*, then:

- Uncheck "control scale remotely"
- Click "connect"
- When the timer starts on the computer screen, go to the BIA scale
  - o Press "Enter/Zero"
  - o Press the down arrow once to select female figure on left side of screen
  - o Press "Enter/Zero"
  - Use the up/down arrows to select age
  - o Press "Enter/Zero"
  - Use the up/down arrows to select height (in cm)
  - o Press "Enter/Zero"
  - o Wait until the arrow on the right-hand side points to "Step on"
  - o Step on the scale
  - o Wait until the computer displays a successful completion
  - o Step off the scale

**NOTE:** Step 3 is only applicable to Tanita Health Ware software that is newly installed. Once Step 3 is completed, it can be omitted during future measurements.

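### Enrolment step B.1 takes a foot-pad body-composition reading in women who are all pregnant, without the pregnancy and device exclusions in the manual's own BIA section

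*Combined protocol and SAP*

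**What the plan says.** The recruitment guidelines for nurses (Mama Bear Clinic Recruitment, section A) approach women in prenatal care who are at "24-32 weeks gestation". At that visit, section B.1 begins with step a: "Utilize the Tanita research study scale provided to measure the participant's weight and body composition". Staff enter age, height, sex and body type, clean the foot pads and put the woman on the scale barefoot. Step f then says: "Print results and record the weight and body composition on the data collection form on the study iPad". A second copy of B.1, placed after the recruitment flyer, repeats the steps, including "Have her step on the scale with her bare feet".

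The section headed Bioelectrical Impedance Analysis, which follows the Data Collector Protocol, defines BIA as an estimate of body composition from electrical impedance. It describes equipment in which "two footpad electrodes (pressure contact) are incorporated into the platform of a precision electronic scale". Under Examinee Preparation it says: "If the participant is pregnant or has a pacemaker or automatic defibrillator, they should be" excluded from the BIA assessment, as REDCap indicates. No visit is named. Step 1 of Measurement Method requires screening questions first and adds: "Weight and BIA are measured at the same time as components of the one-time output method of the Tanita SC-240 instrument".

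The Home Visits text of the Data Collector Protocol, which covers 20 weeks postpartum, is the one place that explicitly tells staff to follow the BIA protocol. The Study Activities Timeline lists weight, blood and urine at about 28 weeks and does not list body composition.

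**The concern.** The manual treats the same kind of measurement in two ways. In the BIA section, pregnancy and implanted cardiac devices are grounds for not taking it. In B.1 it is taken from every woman, all of them pregnant, and the written steps neither ask about a device nor point to the BIA screen.

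Three things are at stake:

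- A woman with a pacemaker or defibrillator has no written protection at enrolment, although the manual gives her one elsewhere.
- If the pregnancy exclusion exists because the reading is invalid in pregnancy, the enrolment values are of doubtful worth. If it exists for safety, it is disregarded for every participant.
- Staff who know both sections have no rule for choosing between them, so enrolment body composition could be recorded for some women and not for others. This is a possibility; the documents do not show it happening.

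**Working it through.** The plan gives no figure on this point, so the check sets the texts side by side.

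1. **Who is measured under B.1.** Section A admits only women in prenatal care at "24-32 weeks gestation". All are therefore pregnant. The Analysis Plan (Aim 3, Statistical Power) has 80 women randomised, and the timeline places randomisation after this visit. At least 80 women would therefore have passed through B.1 if the target is met, and the share that is pregnant is 80/80 = 100%.

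2. **Whether B.1 is a BIA reading.** The BIA section defines BIA as a body-composition estimate and describes foot-pad electrodes and bare feet. B.1 uses foot pads and bare feet and records body composition. B.1 names no model. The only Tanita model named in the manual is the SC-240. Even if the enrolment scale were another model, a foot-pad body-composition reading would still meet the manual's definition.

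3. **Whether the exclusion reaches enrolment.** Its wording is general: it names no visit and makes no exception. Its only explicit invocation is at 20 weeks postpartum. A note under Step 4 of the BIA section mentions a Visit #1, which hints at a wider scope, but the visible text does not define that term.

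4. **Whether B.1 contains a screen.** B.1 has 6 steps (a to f) in each of 2 copies, so 2 × 6 = 12 lines. Steps a and f require body composition, which is 2 × 2 = 4 lines. Lines with a device question or a pointer to the BIA screen: 0 of 12. A.6 says "Then complete all parts of the enrolment interview on the iPad in REDCap". That interview is not in the documents and might hold a device question. It could not settle the pregnancy point, because a screen that applied the pregnancy exclusion would exclude every woman and leave step f undone.

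5. **What the timeline says.** The row for about 28 weeks lists weight, blood and urine. A weight-only B.1 would agree with it; the present B.1 goes beyond it.

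6. **Whether the analysis depends on the reading.** Aim 3 names two main outcomes: days of breastfeeding, and the ratio of weight at 20 weeks postpartum to pre-pregnancy weight. Outcomes that use enrolment body composition: 0 of 2. The Analysis Plan does not mention body composition. The reading could at most be one of the baseline characteristics compared between arms, and enrolment weight would remain available for that.

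**The case against.** The strongest reply concerns scope. B.1 belongs to the nurses' guidelines. The BIA section follows the Data Collector Protocol and is invoked only at the 20-week visit, where its pregnancy clause would catch a woman who is pregnant again. The workflows also differ: B.1 uses a One-Step mode, a clothing preset and a printout, while the BIA section uses computer software and a user profile. On this reading each instruction can be followed at its own visit.

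This stands in part. A reader might infer that the two instructions cannot both be followed. The documents do not establish that, because the BIA section may have been meant for the postpartum visit alone and the undefined Visit #1 is weak evidence against that. The scope reading still leaves a gap. It does not explain why a reading barred in a pregnant woman at 20 weeks postpartum is taken at enrolment, since either a safety or a validity reason would attach to the pregnancy and not to the visit. Nor does it explain why a device is asked about at one visit and not, in the written steps, at the other.

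A second reply is that the absence of a device question cannot be proved, because the enrolment interview and some scripts and consent pages are not visible. That is fair. The point is limited to the written B.1 steps.

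A third reply is that the Analysis Plan's silence on body composition does not show that the measure has no purpose; it does not mention the enrolment blood or urine either. That also stands. The case for weight only rests on the manual's own exclusion and timeline, not on that silence.

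**Conclusion.** The point holds as a minor internal inconsistency. B.1 takes a BIA reading in a group that is 100% pregnant (at least 80 women if the target is met) and has no device screen in its written steps. The BIA section's exclusions, as worded, would cover all of these women, and nothing in the manual exempts enrolment.

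Two stronger inferences are not supported. A reader might infer harm to participants, but the documents do not say whether the pregnancy exclusion is for safety or validity, and they give no number of women with devices. A reader might also infer bias in the trial's results, but neither main outcome uses the reading, so the effect on the main analysis is none.

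The conclusion assumes that the enrolment scale takes a foot-pad impedance reading, which B.1's own steps indicate. It also assumes that no exemption sits in material that is not visible.

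**What to change.** Apply the BIA section's exclusions at enrolment. In both copies of B.1, record weight only: remove body composition from the heading and from steps a and f, and replace the One-Step inputs in step b with a weight-only setting. If the study scale has no such setting, use a clinic scale. The method needs to be written out, because the manual says the SC-240 takes weight and BIA together. This brings B.1 into line with the timeline.

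If the team wants the reading in pregnancy, amend Examinee Preparation to say that the pregnancy exclusion does not apply at enrolment, and why. In either case, ask the pacemaker and defibrillator question before any BIA reading under B.1, and take weight only from a woman who answers yes.

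The editing cost is a few lines in two copies, with no extra visit or staff. The weight-only option gives up enrolment body composition. If a clinic scale is used, it also gives up weighing on the same instrument at enrolment and at 20 weeks, although enrolment weight does not enter the weight-retention ratio. Keeping the reading costs a written justification and one question per woman.

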#### C. Transporting Specimens

- 1. Towards the end of the work day, call the [name] lab contact number to inform the staff that Mama Bear study specimens will be delivered. Give an approximate time of arrival.
- 2. Place all research specimens collected for the day in the cooler provider.

Version Number 1 Date

[figure not shown]

3. Transport the specimens, by car, to [name] and pull into a space along the curb in front of the entrance. Call the lab the notify them of your arrival. Carry the specimen into the front lobby and hand to the lab representative.

Version	Number 1
---------	----------

(alternative: Mana Bear 031017\_4) The Mama Bear Flyer with description Mama Bear 031017\_4

The Mama Bear flyer (as shown below) is used by nurses when approaching patients in the clinic to see if they are interested in meeting with research staff. For more information, see Mama Bear Recruitment Procedures, Section A 3.

Mama Bear helps moms reach their breastfeeding goals and lose weight after giving birth.

Help moms like you have a healthy future. Join the Mama Bear research study today! Call: [contact] Email: [contact]

Front

ne as headle

- B. Obtaining Weight, Body Composition, Blood and Urine Specimens (for all handling of biological fluids, use gloves, and employ good hand washing techniques)
  - 1. Weight and Body Composition
    - a. Utilize the Tanita research study scale provided to measure the participant's weight and body composition.
    - b. Select "One-Step" Mode and input required data:
      - o Enter weight of clothing- 1.0 kg (preset)
      - o Enter Study ID number
      - o Enter Body type- "Standard"

- o Enter Gender- Female
- o Enter age
- o Enter height
- c. Have the participant remove any outerwear garments (coat, hat, scarf, gloves), and remove her socks or stockings.
- d. In the presence of the participant, clean the foot pads on the scale with alcohol wipes
- e. Have her step on the scale with her bare feet.
- f. Print results and record the weight and body composition on the data collection form on the study iPad.
- 2. Blood
  - a. Use the labels provided to write the ID number, date and time of the blood collection
  - b. Place one label on the red top tube, and one on the lavender top tube.
  - c. Hand both tubes to the participant ask her to take them with her to the lab so that her blood can be collected in these tubes at the same time that she is getting her blood drawn for the blood sugar test.
  - d. When the participant returns with the blood filled tubes, place them in a specimen collection bag, seal, and place the bag in the refrigerator.
- 3. Urine
  - a. Use the label provided to write the ID number, date and time of the urine specimen collection. b. Place the label on a urine vial provided for the study.
  - c. Have the participant hand you the cup with her freshly voided urine once she steps out of the restroom.
  - d. Pour a small amount of that urine into the pre-labelled urine vial and cap tightly.
  - e. Return the original cup of urine for testing with the dipstick.
  - f. Place the study urine vial in the bio-storage bag, close and seal, and then put the urine specimen into the refrigerator.

